For the functional measures used, we will assess both cross-sectional and lagged associations with pathological measures using the combined data from HD-YAS 1.0 and HD-YAS 2.0. To test cross-sectional associations, we will add the contemporary pathological measures as additional potential predictors in the cross-sectional models of the form defined above for hypothesis 1. These analyses will be limited to only the HD gene carriers and will therefore not include terms for HD-carrier versus control status or interactions of that genetic status.

We will further test for a potential lag between pathological events and measurable impairment using only the cross-sectional data impairment data from HD-YAS 2.0. Analyses will be limited to those from the HD-YAS 1.0 who also participated in HD-YAS 2.0. With single HD-YAS 2.0 functional observations per participant, we will estimate ordinary least squares regression models using both the baseline and follow-up (HD-YAS 2.0) pathology measures. (Subject to potential adjustments for violation of mathematical modeling assumptions as discussed in the General Methods section above). We will test for an association between HD-YAS 1.0 pathology measures and HD-YAS 2.0 functional measures. We will further estimate the joint associations of the HD-YAS 1.0 and HD-YAS 2.0 pathology measures by including both as joint predictors of the functional outcome. We will also refit the models by re-parameterizing the 1.0 and 2.0 values as the 1.0 value and the change in the pathology measure between 1.0 and 2.0. Other covariates in these models will be the same as described for the previous analyses (age, sex, CAG length, CAG by age interaction, and in the case of cognitive functional measures, baseline NART and Education level scores).

Within the premanifest HD gene carrier group, we will determine how well the clinical and neuroimaging variables are predicted by CSF levels of mHTT and by CSF and plasma levels of NfL. Analyses will be performed one biomarker one at a time and have the general form:

$$y = b_0 + b_1 * \text{biomarker} + b_2 * \text{age} + b_3 * \text{gender} \\ + b_4 * \text{age} * \text{gender} + b_5 * \text{IQ} + r_{\text{subject}} + e$$

Additionally, we will assess evidence of longitudinal prediction of change in HD measures by adding the additional terms to the above model.

$$\begin{aligned} & \text{follow-up} * (a_1 + a_2 * \text{CAG} + a_3 * \text{age} + a_4 * \text{CAG} * \text{age}) + \\ & \text{follow-up} * (a_5 * \text{baseline biomarker}) + a_6 * \text{biomarker change from baseline}, \end{aligned}$$

Hypothesis 4: Individuals with higher levels of somatic CAG-repeat expansion are more vulnerable to early striatal atrophy, breakdown of corticostriatal connections and cortical pathology.

We will analyse potential relationships between somatic expansion and other HD measures using the same models described immediately above for hypothesis 3.

Hypothesis 5: Measures identified as showing disease sensitivity in hypotheses 1 and 2 have utility for future trials of disease-modifying therapy in premanifest HD gene carriers.

We will calculate nominal sample size estimates for longitudinal measures showing relationship to HD gene expansion vs. controls or longitudinal relationships to the severity of combined age and CAG genetic risk. We will perform such calculations for measures with longitudinal change below the 15% estimated false discovery rate. We note however, that this screening for evidence of disease sensitivity will tend to optimistically bias such estimates towards smaller sample sizes. The resultant sample sizes will therefore represent an estimated lower bound.

We will consider the following 5 biomarkers as primary outcomes for these analyses, as previous data, including baseline data from YAS 1 have suggested cross-sectional relationships between these measures and early HD disease pathology:

1. Putamen volume change
2. Caudate volume BSI
3. CSF NfL levels
4. Plasma NfL levels

5. CSF mHTT levels

Estimates of sample size requirements will be based upon the estimated longitudinal effect sizes (mean slope divided by between-subject slope standard deviation) calculated from mixed effect longitudinal. The models will be limited to HD gene-expanded participants and follow-up time will be the sole fixed effect. (The resultant estimates of natural history change will thus represent the relevant average natural history progression among the entire group of CAG-expanded participants. Additional effects of potential stratification are discussed shortly below.) Initial calculations will assume 5- and 10-year trials with annual follow-up, 50 and 70% slowing due to treatment, no placebo effect, and use of slopes rather than net change of outcome from the beginning to end of the trials. We will assume no drop-out and that the within-subject outcome variance does not increase over time. These conditions will yield best-case estimates for idealized trials. For any measure, should the resultant sample sizes appear hypothetically feasible, we will perform follow-up calculations assuming 2-, 3-, and 4-year trials with similar and smaller treatment effect sizes.

Potential trial enrichment: For the potential trial outcomes used in the above analyses, we will further test whether the possible stratification criteria of HD-ISS stage of 1 or greater (versus 0) or CAP100 score of 100 or greater are significantly associated with different rates of natural history longitudinal change. We will repeat the sample size analyses described in the previous paragraph with the data limited to the subset of CAG-expanded participants meeting the stratification criterion in question.

Table 1: Outcome variables by modality

Neuroimaging	
Regional brain volume
 
 • Whole brain (cross-sectional volume and change YAS 1-2) • Putamen (plus HD-ISS classification) • Caudate (cross-sectional volume and change YAS 1-2) (plus HD-ISS classification) • Ventricles (cross-sectional volume and change YAS 1-2) • Grey matter (cross-sectional volume and change YAS 1-2) • White matter (cross-sectional volume and change YAS 1-2) 
Structural brain connectivity
 
 • 6 cortico-striatal connectome • 14 corticocortical connectome 
NODDI
 
 • Fractional Anisotropy • Mean Diffusivity • Radial Diffusivity • Orientation Dispersion Index • Neurite Density Index 
MPM
 
 • R1(iron & myelin) • R2* (iron/oligos) • MT (myelin)
Cognitive/emotional function	
Cognitive Flexibility
 
 • IED ED Shift Errors • IED Failures at Stage 8 
Processing Speed
 
 • SDMT (total correct) (plus HD-ISS classification) 
Verbal Fluency
 
 • Animals (total correct) 
Interference
 
 • Stroop Interference (total correct) 
Inhibition
 
 • Stop Signal Reaction Time 
Emotion Cognition
 
 • Intensity Morphing Decreasing (Negative Emotions only) • Moral Emotions Agent Guilt Score 
Planning
 
 • OTS Minimum Move solutions

	
Learning
 
 • IED pre-ED Errors • IED ED reversal errors 
Attention
 
 • RVP A' • RVP Mean Latency (for correct trials) 
Memory
 
 • PAL Total Errors Adj • SWM between errors 
Motivation
 
 • Goals Prior Assay Task Slope
Neuropsychiatric function	
State/Trait Anxiety (STAI)
 
 • State anxiety • Trait anxiety 
Zung self-rating depression scale (SDS)
 
 • Total score 
Barratt Impulsivity scale (BIS-11)
 
 • Total score 
Frontal systems behaviour scale (FrSBE)
 
 • Apathy • Disinhibition • Executive function 
Apathy motivation index (AMI)
 
 • Total score 
Obsessive-Compulsive Inventory (OCI-R)
 
 • Total score 
Pittsburgh Sleep Quality Index (PSQI)
 
 • Total score 
MOS 36-Item Short-Form Health Survey (SF-36)
 
 • Physical functioning • Limitations due to physical health • Limitations due to emotional problems • Energy/fatigue • Emotional well-being • Social functioning • Pain

	
 • General health
Clinical	
 • Total Motor Score (TMS)
Functional	
 • Total Functional Capacity (TFC) • Independence Scale (IS)
Biofluid markers	
CSF
 
 • Mutant HTT (logfM) • Total HTT (log fM) • NfL • Tau • YKL-40 • IL-6 • IL-8 • GFAP • UCHL-1 
Plasma
 
 • NfL • (also GFAP, Tau, UCHL-1 included in Quanterix Neurology 4PlexA with NfL) 
Blood
 
 • DNA - somatic CAG-repeat expansion (YAS 1 and YAS 2)

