Approximately 4.5 years after baseline 57 premanifest HD gene carriers (89% retention) and 45 healthy controls (67% retention) returned for a follow-up visit (HD-YAS 2.0). An additional 23 new participants were recruited: 9 premanifest HD gene carriers and 14 controls. The full cohort consists of 66 premanifest HD gene carriers and 59 healthy controls, matched for age, gender and education. All participants completed the clinical and cognitive assessments, 91% had MRI and 86% underwent CSF collection. The cohort will be characterised in terms of the new Huntington's Disease Integrated Staging System (HD-ISS) (Tabrizi *et al*, 2022), which incorporates disease pathology and biomarkers within staging classification. In addition, predicted years to clinical onset will be linked to standardisation of the CAG-Age-Product (CAP) score via previously described statistically modelling of CAP=100 at the expected age of diagnosis (Warner *et al*, 2022). These measures will be important for disease staging in future clinical trials.

General Methods

Measures

Approximately 70 individual variables from various measurement domains will be

analysed as outcome variables that may differ between the premanifest HD gene carriers and controls. The majority of measures are identical to baseline, with a few exceptions:

- One cognitive task, the breakpoint assessment, was removed from the battery due to feedback from participants. A novel task, The Goals Prior Assay, was introduced to capture the motivational domain.
- Neurogranin, a marker of synaptic function, was not assessed at this timepoint. There was no significant difference in CSF neurogranin concentration between the premanifest HD gene carrier and control groups at baseline in HD-YAS.
- Total huntingtin (tHTT) was not assessed at this timepoint. At baseline, the presence of the mutant HTT gene did not have any effect on tHTT concentrations; tHTT concentrations in CSF were unchanged in premanifest HD gene carriers.
- Volumetric neuroimaging measures, in addition to cross-sectional measures at this timepoint, include a direct measure of change, the boundary shift integral (BSI). This method has shown greater sensitivity to subtle longitudinal volumetric change than independent volume measures at each timepoint (Freeborough and Fox).
- We have included a measure of CAG-repeat expansion derived from blood DNA. This will be assessed using both the HD-YAS 1.0 and HD-YAS 2.0 samples.

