Outliers will be judged by both observed and residual values from the models. Extreme outliers with high model leverage will be queried with the data sources for accuracy. (The sources will not be given information about the type of influence such outliers exert on the analyses.) Outliers judged due to mistakes or poor-quality data will be excluded from analyses. Outliers confirmed to be accurate measurements will trigger a sensitivity analysis by refitting the relevant model with the outlier removed. Unless this reanalysis clearly demonstrates an absence of group or CAG effect, regardless of outlying data, we will perform nonparametric bootstrapping of the original analyses and report estimates and inference based on bias-corrected, accelerated confidence intervals.

Missing data

If more than 10% of data for any measure within an analysis (predictor or outcome) is missing, then we will use multiple imputations for parameter estimation and inference. We will also include a specific assessment of the plausibility of the missing at random (MAR) assumption that would justify this procedure. The imputation will be based on both the other variables being used in the analysis and also on other outcome variables that show a notable correlation with the variable in question when the values are not missing.

Analysis of drop-out effects

An exception to the use of multiple imputation will occur in the case of participant drop-out when longitudinal mixed effect models are fit, except if there is reason to suspect that the MAR assumption only holds conditionally after considering other available baseline measurements not used explicitly in the longitudinal model. Otherwise, correction for potential MAR dropouts will be done by including baseline values for those who dropped out within the modelling data. (This missing data strategy works only for random effect longitudinal models.) Similarly, the single measurements available from replacement participants will also be used in fitting the longitudinal models. This is consistent with the assumption that the original and replacement participants form random samples from the same underlying population of interest. It is known that approximately 30 of the original 131 participants dropped out. The majority of these were in the control group. Approximately the same number of new participants have been added to the study and will have a single, recent set of measurements available.

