measurements collected in HD-YAS 2.0. Unless otherwise noted, outcomes are continuous or pseudo-continuous measures. By default, we will use general least-square linear models to evaluate possible overall group differences and age interactions between the young adult premanifest HD gene carriers and controls. Within these same models, we will control and test possible CAG-length-driven differences within premanifest HD gene carriers. Covariates will include age, gender, site and age interactions with gender. The main hypothesis of group differences will be evaluated by least-square means.

The primary cross-sectional analyses model will have a nearly identical generic form to that used in the original baseline analysis:

$$y = b_0 + I_{pHD} * (b_1 + b_2 * CAG + b_3 * age + b_4 * CAG * age) + b_5 * age + b_6 * sex + b_7 * age * sex + b_8 * NART + b_9 * EducLevel + r_{subject} + e$$

where y is an outcome variable, $I_{pHD} = 1$ if a participant is from the premanifest HD gene carrier group and 0 otherwise, the b 's are linear regression coefficients, $r_{subject}$ is a subject-specific random effect applicable to participants who have had two measurements, and e is the residual random error term. Both $r_{subject}$ and e are assumed to be independently, identically normally distributed among the participants with 0 mean. (See above for contingencies when these distributional assumptions prove empirically untenable.) Note that NART score (a proxy for estimated baseline IQ) and education level will only be used for cognitive outcomes.

Hypothesis 2: There is evidence of disease-related *longitudinal* change ~20 years from expected symptom onset in: a) brain imaging; b) cognition; c) neuropsychiatric function; and d) biofluid measures.

The longitudinal analyses will build on the above model by adding these further regression terms:

$$a_0 * follow-up + I_{pHD} * follow-up * (a_1 + a_2 * CAG + a_3 * age + a_4 * CAG * age) + follow-up * (a_5 * age + a_6 * sex + a_7 * age * sex + a_8 * IQ,)$$

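### The SAP queries an extreme outlier with the data source only if it also has high leverage, a filter that does not select the errors that move the carrier-control contrast

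*SAP*

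**What the plan says.** The Outliers paragraph in the SAP's General Methods has four steps.

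- **Detection:** "Outliers will be judged by both observed and residual values from the models". No numerical cut-off is given.
- **Query:** "Extreme outliers with high model leverage will be queried with the data sources for accuracy". The value must be extreme and must also have high leverage; neither term is defined. The query is blinded: "The sources will not be given information about the type of influence such outliers exert on the analyses".
- **Exclusion:** "Outliers judged due to mistakes or poor-quality data will be excluded from analyses".
- **Refit:** "Outliers confirmed to be accurate measurements will trigger a sensitivity analysis by refitting the relevant model with the outlier removed". Unless the refit clearly shows no effect, the analysis moves to bootstrap inference.

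The exclusion and refit sentences carry no leverage condition. The query is the only step named for finding out whether a value is right.

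Under Hypothesis 1 the model contains "I_{pHD} * (b_1 + b_2 * CAG + b_3 * age + b_4 * CAG * age") plus age, sex and their interaction, with NART and education added for cognitive outcomes only. On the test itself the SAP says: "The main hypothesis of group differences will be evaluated by least-square means".

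**The concern.** Leverage marks participants with unusual combinations of age and CAG. It says nothing about whether the outcome is wrong. The group contrast, evaluated near average covariates, gives each participant a weight of roughly one over the group size, so a gross entry or assay error in someone of ordinary age and CAG is as harmful to it as one in someone unusual. Read literally, the rule sends the second to the source and not the first.

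Three things are at stake. Wrong values may stay in the main contrasts, shifting the estimate and inflating the residual variance, so that power is lost. The carrier model has CAG terms that controls do not have, so high leverage is commoner among carriers and the two groups would be cleaned with different intensity. And because neither extreme nor high leverage has a cut-off, two analysts could apply the rule differently in a plan meant to prespecify the analyses.

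**Working it through.** The documents give no query rate or cut-off, so there is no stated figure to reproduce.

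**Inputs from the documents.** "The full cohort consists of 66 premanifest HD gene carriers and 59 healthy controls" (SAP, The Cohort), so n = 125. The Hypothesis 1 equation has p = 8 fixed coefficients, or 10 for cognitive outcomes. There are about 70 outcomes (SAP, Measures). Ages run from 18 to 47 (protocol section 6). The 0.53 SD effect is the one in the baseline power statement (protocol section 8).

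**Assumptions.** Age uniform on 18-47 or normal (mean 33, SD 5.6); CAG geometric from 40 or normal (mean 42.5, SD 1.7); age x (CAG - 35.5) at most 370; one record per participant; high leverage means a hat value above 2p/n (alternative 3p/n).

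**1. Who would be queried.** The hat value is h_i = x_i'(X'X)^-1 x_i, which contains no outcome. The 2p/n cut is 16/125 = 0.128 for p = 8 and 20/125 = 0.160 for p = 10. Over simulated designs:

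| | above 2p/n | above 3p/n |
|---|---|---|
| p = 8 | 5.9% to 9.4% | 1.7% to 3.3% |
| p = 10 | 4.6% to 7.2% | 0.9% to 2.1% |

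So 91% to 95% of participants fall below 2p/n, and 97% to 99% below 3p/n. For p = 8 the share above 2p/n is 9% to 14% of carriers but only between under 1% and about 4% of controls, depending on the assumed covariates.

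**2. Does leverage pick out the errors that matter?** The weights on the group contrast are about 1/66 and 1/59, so their absolute values sum to about 2 and average 2/125 = 0.016. A 5-SD error therefore moves the contrast by about 5 x 0.016 = 0.08 SD on average. In the simulated designs this is 0.43 to 0.44 standard errors at ordinary leverage and 0.38 to 0.43 at high leverage. Of the tenth of participants with the most weight on the contrast, 77% to 91% have ordinary leverage.

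**3. Effect of one unqueried error (single-record model, 66/59, p = 8).** Take a control of ordinary leverage with a 5-SD error that opposes the true difference.

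- Shift: 5/59 = 0.085 SD.
- Clean standard error: about 0.182 SD. Residual variance becomes about 1 + 25 x 0.94/117 = 1.20, so the reported standard error is 0.182 x sqrt(1.20) = 0.200.
- Power without the error: Phi((0.53 - 1.98 x 0.182)/0.182) = Phi(0.93) = 82%.
- Power with it: Phi((0.53 - 0.085 - 1.98 x 0.200)/0.182) = Phi(0.27) = 61%.

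Simulation gives 79% to 83% without the error and 56% to 63% with it. The null rejection rate stays at 4% to 5%.

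**4. The pooled model.** Hypothesis 1 pools both visits: 131 + 125 = 256 records on 131 + 23 = 154 people (73 carriers, 81 controls), with a subject random effect. For within-subject correlations of 0.3 to 0.9 (assumed), a 10-SD error in one control record moves the contrast by about 0.06 to 0.07 SD if that person has two visits and 0.10 to 0.12 SD if one, against 10/59 = 0.17 SD in the single-record model. Halve these for a 5-SD error.

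**5. Query load without the leverage condition.** Expected flags in clean data are 125 x P(|r| > c) x 70.

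- c = 3: 125 x 0.0027 x 70 = 24 (normal), or 125 x 0.0033 x 70 = 29 (t with 116 degrees of freedom, the reference for externally studentised residuals).
- c = 3.5: 125 x 0.000465 x 70 = 4, or 125 x 0.00066 x 70 = 6.
- With the 2p/n condition kept at c = 3: 24 x 0.046 to 24 x 0.094, or about 1 to 2.

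**The case against.** **Leverage may be meant loosely.** The sentence after the rule speaks of the influence outliers exert. If the authors mean influence, the examples above are caught: with Cook's distance above 4/n = 0.032, a 5-SD error in an ordinary-leverage control was flagged in 99% of simulated datasets. This is a fair reading, but the SAP does not state it, and the literal term means something else.

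**Other checks exist.** The SAP plans ranges and plots for all measures; the protocol has CSF cell-count flags (Sample Quality Control), direct tablet capture of CANTAB and EMOTICOM, and data monitoring (sections 11 and 16). A gross error may well be seen. None of these provisions names a source query for an extreme value, however, and the SAP's remedies for assumption violations change the model or the inference without verifying the value.

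**Stronger readings that the documents do not support.** A reader might infer that more than nine tenths of all values are never checked. That is the wrong denominator: the rule concerns extreme outliers, and any sensible rule leaves almost all values unqueried. A reader might also infer that an ordinary-leverage outlier cannot be excluded or refitted. Those two sentences carry no leverage condition, and the SAP does not say that a source query is the only way to judge a mistake. A reader might, finally, take a 10-SD opposing error (power falling from about 80% to about 22% to 25%) as the expected harm. That is a chosen worst case in a single-record model, which is not the model planned for Hypothesis 1.

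**Conclusion.** The point holds in a limited form. As worded, the only verification step the SAP names does not reach an extreme value at ordinary leverage. That describes about 91% to 95% of participants at an assumed 2p/n cut: nearly all controls and about nine in ten carriers. Leverage does not separate harmful from harmless errors for the group contrast, and the filter makes cleaning uneven between the groups.

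The size of the harm rests on assumed error sizes and covariate distributions. One opposing 5-SD error takes power at 0.53 SD from about 80% to about 60% in a single-record 66/59 analysis. The pooled Hypothesis 1 model is less affected. The boundary shift analyses do use one record per person, on at most 57 carriers and 45 controls; a single-record simulation with those numbers (p = 8) gave about 72% falling to 41%. An error in the direction of the effect would exaggerate the estimate instead. Type I error is not inflated. The change is cheap and worth making before the analyses are run.

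**What to change.** Delete the leverage condition so that every extreme outlier is queried, and keep the existing provision that sources are not told how the value affects the results. Define extreme by a stated residual cut-off, for example an absolute externally studentised residual above 3.5 (or 3). Apply the same trigger to the refit without the outlier. If the authors meant influence, they should say so and name the measure and its cut-off.

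Do not use DFBETA above 2/sqrt(n) as a stand-alone trigger. It flags about 6 to 7 participants per outcome for the group term in clean data, or some 420 to 490 over 70 outcomes. Because a refit usually leads on to bootstrapping under the SAP, nearly every analysis could end up bootstrapped with no error present.

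The cost is one phrase and about 4 to 6 queries (cut-off 3.5) or 24 to 29 (cut-off 3) over about 70 outcomes with normal residuals. Heavy-tailed outcomes will produce more, and screening all 256 pooled records instead of 125 would roughly double the count (256/125 = 2.05).

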#### **UHDRS Total Functional Capacity Scale (TFC)**

The TFC represents the Investigator's assessment of the participant's capacity to perform a wide range of activities of daily living including working, chores, managing finances, eating, dressing and bathing. It is based on a brief interview with the participant and the study partner (if relevant). Scores range from 0 to 13, and higher scores represent better functioning.

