Huntington's Disease Young Adult Study 2.0

5th December 2023

HD-YAS 2.0 SAP 5th December 2023

Overview:

The Huntington's Disease Young Adult Study (HD-YAS) is part of the Wellcome Trust funded TREAT-HD programme, which aims to deliver therapies to prevent neurodegeneration in HD. In parallel to exploring novel therapeutic strategies in HD, HD-YAS aims to identify the optimum time window to deliver preventative treatments. Specifically, it seeks to determine early systems-level pathology in very early premanifest HD gene carriers, and to assess the impact of this degeneration on symptomatology. From 2017 to 2019 a cohort of 64 premanifest HD gene carriers approximately 24 years from expected symptom onset and 67 matched controls underwent clinical, cognitive, neuropsychiatric, neuroimaging and biofluid assessments (Scahill *et al*, 2020). There was no evidence of disease-related functional impairment. No significant differences in brain structure and function were evident between gene carriers and controls with the exception of smaller striatal volumes. Neurofilament light (NfL), a marker of neuronal damage, was elevated in gene carriers, with higher levels in those closest to expected symptom onset. HD-YAS 2.0 provides follow up approximately 4.5 years after baseline with the aim of determining whether ongoing longitudinal degeneration is evident and whether this impacts function. We will determine this by addressing the following hypotheses:

Hypothesis 1: There is evidence of a disease-related measurable phenotype ~20 years from expected symptom onset in:

- a) brain imaging;
- b) cognition;
- c) neuropsychiatric function; and
- d) biofluid measures.

Hypothesis 2: There is evidence of disease-related *longitudinal* change ~20 years from expected symptom onset in:

- a) brain imaging;
- b) cognition;

- c) neuropsychiatric function; and
- d) biofluid measures.

Hypothesis 3: Early pathological events lead to impairment in isolated functional domains such as cognitive flexibility.

Hypothesis 4: Individuals with higher levels of somatic CAG-repeat expansion are more vulnerable to early striatal atrophy, breakdown of corticostriatal connections and cortical pathology.

Hypothesis 5: Measures identified as showing disease sensitivity in hypotheses 1 and 2 have utility for future trials of disease-modifying therapy in premanifest HD gene carriers.

The Cohort

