Violation of model distribution assumptions

For the default general linear models, the key standard assumptions are that residuals of the outcome variable will be approximately normally distributed, independent of the predicted values, and with uniform variance. The assumption is most commonly violated when the residuals show notable skewness. In such cases we will first evaluate whether the assumptions are reasonably satisfied by a square-root, log, polynomial, or inverse

transformation of the outcome, in which cases the analysis will proceed with the transformed variable. Such transformations are most commonly unsatisfactory due to floor or ceiling effects in the range of measurement of the outcome. In such cases we will consider the feasibility of using an ordinal logistic model or a censored model. If neither of these is practical and satisfactory, then the model will be subjected to bootstrapping as described above for outliers. If residual variance changes systematically by value of a covariate (e.g. age) then we will fit the models using iteratively reweighted least-squares, with weighting based on the relevant covariate.

Multiple testing

The issue of multiplicity in outcomes will be addressed by calculating estimated false discovery rates (FDR) for the covariate-adjusted difference between premanifest HD gene carriers and controls. We will perform the FDR analyses at the domain level. (Rigor is not diminished by performing these calculations at the domain level rather than in a single appraisal of the combined domains. Unlike correction for family-wise error rate, FDR calculations depend on the distribution but not on the number of hypothesis test p values considered simultaneously.) One cognitive measure, the CANTAB *inter-extra dimensional shift* task (IED), will be treated as a confirmatory rather than exploratory analysis, based on previous data showing HE differences far from onset. Significance tests will be taken at face value for this test, and it will not be included in the false discovery corrections.

Hypothesis Testing

Hypothesis 1: There is evidence of a disease-related measurable phenotype ~20 years from expected symptom onset in: a) brain imaging; b) cognition; c) neuropsychiatric function; and d) biofluid measures.

A repetition of the cross-sectional analyses performed in HD-YAS 1.0 will be performed, using the additional statistical power provided by the repeated or new subject

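### For sparse floor or ceiling outcomes the SAP's last resort, a BCa bootstrap of the mean difference, is anti-conservative: nominal 5% becomes about 8–11% if 2–5% of each group is off the ceiling

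*SAP*

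**What the plan says.** Under Violation of model distribution assumptions, the SAP first tries transforming a skewed outcome and recognises that floor or ceiling effects are the usual reason this fails. Next: "In such cases we will consider the feasibility of using an ordinal logistic model or a censored model". Then the last resort: "If neither of these is practical and satisfactory, then the model will be subjected to bootstrapping as described above for outliers". The Outliers paragraph defines that bootstrap as nonparametric, with estimates and inference taken from BCa confidence intervals. The SAP sets no minimum number of off-ceiling values and no rule for a group without variance, and names no exact, permutation or penalised alternative.

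TFC and the Independence Scale form the Functional row of SAP Table 1. The protocol says of TFC: "Scores range from 0 to 13, and higher scores represent better functioning". It gives the Independence Scale a maximum of 100. Of the cohort at baseline, the SAP Overview says: "There was no evidence of disease-related functional impairment".

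On numbers, SAP The Cohort states: "The full cohort consists of 66 premanifest HD gene carriers and 59 healthy controls". It adds: "All participants completed the clinical and cognitive assessments". If TFC counts among the clinical assessments, the multiple-imputation rule is not triggered at this visit.

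**The concern.** In a premanifest cohort with intact function, nearly everyone may score the maximum on TFC and the Independence Scale. If every control does so, the group effect is separated: its maximum-likelihood estimate is infinite in the ordinal model, and the control mean of the censored model is not estimable. The SAP's sequence then leads to the bootstrap in the situation where it works worst. Resampling a constant group always returns the same constant, so the interval reflects only the few off-ceiling people in the other group.

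The SAP aims to establish whether ongoing degeneration affects function. Hypothesis 3 carries forward only functional measures that differ between groups, so a false TFC difference could pass that screen. The Functional domain has two measures, so domain-level FDR offers little protection. A BCa interval also does not by itself supply the p value that the FDR step needs.

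**Working it through.** **Inputs.** HD-YAS 2.0 (SAP, The Cohort): 57 + 9 = 66 carriers, 45 + 14 = 59 controls. The Hypothesis 1 model pools both visits with a subject random effect, so the participants analysed are 64 + 9 = 73 carriers and 67 + 14 = 81 controls. The 5% error rate is from protocol section 8; two-sided testing is assumed, and the SAP states no confidence level. Off-ceiling counts and probabilities are assumptions. Each participant is reduced to off ceiling yes/no, one point below maximum, without covariates.

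**Plan's own figure.** The SAP gives no error rate for this fallback. The cohort figures reproduce: 57/64 = 89%, 45/67 = 67%, totals 66 and 59.

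**Why the interval is short.** With m of n carriers off ceiling and no controls, a resample gives a zero difference only if none of the m is drawn, with probability ((n − m)/n)^n.

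- 4 of 66: (62/66)^66 = 0.016
- 4 of 73: (69/73)^73 = 0.016
- 3 of 66: (63/66)^66 = 0.046

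The lower BCa limit sits at bootstrap quantile Φ(z0 + (z0 − 1.96)/(1 − a(z0 − 1.96))), where z0 is the bias correction and a the acceleration. Zero is excluded when this quantile exceeds the probability above. The value of z0 depends on whether resamples equal to the estimate count half or not at all (strict). For 66 v 59:

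| Split | Ties | z0 | a | Lower quantile | P(zero) | Excludes 0? |
|---|---|---|---|---|---|---|
| 3 v 0 | half | 0.084 | 0.090 | 0.064 | 0.046 | yes |
| 3 v 0 | strict | −0.204 | 0.090 | 0.022 | 0.046 | no |
| 4 v 0 | half | 0.073 | 0.076 | 0.057 | 0.016 | yes |
| 4 v 0 | strict | −0.181 | 0.076 | 0.022 | 0.016 | yes |

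The 4 v 0 interval is 0.015 to 0.136 points (half) or 0.015 to 0.121 (strict). For 4 v 1 it is −0.019 to about 0.12, which includes zero. On 73 v 81 the same three conclusions hold.

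**Fisher comparison.** For 4 v 0 on 66 v 59, the two-sided p is [C(66,4) + C(59,4)]/C(125,4) = (720,720 + 455,126)/9,691,375 = 0.12. On 73 v 81 it is C(73,4)/C(154,4) = 1,088,430/22,533,126 = 0.048, because the opposite extreme is more probable and does not count. For 3 v 0 the values are 0.25 and 0.10.

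**Conditional error.** Given exactly four off-ceiling people and no true difference, all four fall in one group with probability 0.12 on 66 v 59, and (1,088,430 + 1,663,740)/22,533,126 = 0.12 on 73 v 81. The BCa interval calls both extremes significant, so the conditional error is at least 12%.

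**Overall error.** Let both groups have off-ceiling probability p. The error is the sum over all (a, b) of Bin(a; n1, p) × Bin(b; n2, p) × [BCa interval excludes 0]. With ties counted half:

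| p | 66 v 59 | 73 v 81 |
|---|---|---|
| 2% | 7.8% | 9.3% |
| 3% | 10.1% | 10.5% |
| 5% | about 10% | about 9% |

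Strict counting gives somewhat higher rates, up to about 13%. At p = 1% on 66 v 59 the error is 2.7% with half counting and about 6% with strict, so there the answer depends on the tie rule.

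**With covariates.** Case-bootstrapping the Hypothesis 1 model without NART and education, on simulated covariates for 66 v 59, gives 6–8%, 10–11% and 10–12% at p = 2%, 3% and 5%. A pooled two-visit simulation gives 7–12%. A covariate-adjusted permutation test on 66 v 59 rejects 3.7–4.5%, and Fisher 1–3%.

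**The case against.** A reader might infer that the plan will usually report a functional deficit in carriers. The documents do not support that. They give no TFC or Independence Scale distribution, so any split is hypothetical. One off-ceiling control removes the 4 v 0 result. On the pooled participants, which is the SAP's cross-sectional dataset, Fisher also reaches 0.048 for 4 v 0, so that example does not separate a valid test from an invalid one. Fisher is also the most conservative comparator: on 66 v 59 the same split gives 0.045 (Welch), 0.055 (pooled t), 0.066 (unadjusted Firth) and 0.084 (Boschloo).

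The bootstrap is reached only after transformation, ordinal and censored models have been set aside, and the SAP does not rule out a penalised ordinal fit. The Outliers paragraph also skips the bootstrap if refitting without the outliers clearly shows no effect. The SAP does not say whether that condition carries over; here, dropping the off-ceiling values would leave a constant outcome. BCa is not the only weak step either: a likelihood-ratio test from a retained ordinal model gives p of about 0.02 for 4 v 0 on 66 v 59.

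A reader might also extend the point to "IED Failures at Stage 8". Nothing in the documents shows that this outcome is sparse, and a yes/no outcome does not imply separation.

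Finally, Hypotheses 1 and 2 do not name the Functional domain, TFC and the Independence Scale are not among the five primary biomarkers of Hypothesis 5, and the planned descriptive tables would let a careful reader see that a difference rests on a few people.

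These points limit the concern to a conditional one of moderate size. They do not remove it: the inflated error rate does not depend on the choice of split, on Fisher, or on which of the two sample sizes is used.

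**Conclusion.** The concern holds in a limited form. If a sparse ceiling outcome reaches the SAP's last resort, the BCa interval is too short, and a nominal 5% test rejects about 8–11% of the time when both groups have an equal 2–5% chance of being off ceiling. This is so for 66 v 59 and for 73 v 81. At about 1% the result depends on tie handling.

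The size rests on the assumed off-ceiling probabilities, a 95% interval, ties counted half, and the ordinal and censored models having been rejected, which is likely under separation. The 73 v 81 sum also treats each participant as one value, although 57/73 = 78% of carriers and only 45/81 = 56% of controls have two visits. TFC and the Independence Scale are plausible cases, not demonstrated ones.

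**What to change.** Add to Violation of model distribution assumptions: where 90% or more of either group sits at one value, the bootstrap of the mean is replaced by one named test, chosen before the data are seen. Either of these would serve:

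- a permutation test of the adjusted group difference, permuting whole participants within strata of visits attended; or
- Firth penalised logistic regression on off-ceiling yes/no, with a reduced covariate set.

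If Firth is chosen, the SAP should also say how two visits become one record per participant, given the unequal share with two visits.

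Report the off-ceiling counts by group, and use the resulting p value in the domain FDR step. Apply the rule to TFC and the Independence Scale. Apply it to IED stage-8 failure only if that outcome meets the 90% trigger, and keep IED outside the FDR step, as Multiple testing already states.

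The cost is a sentence or two in the SAP, a small amount of programming, and less power for sparse ceiling outcomes.
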